### 12.6.2.5 Risk Markers

The risk markers are:

- Systolic and diastolic blood pressure on Day 0, Day 6, Day 30 Visit, Day 60 Visit, and Day 90 Visit.
- hs-CRP, homocysteine, blood glucose, LDL, HDL, TG, and TC in serum on Day 0, Day 30 Visit, Day 60 Visit, and Day 90 Visit.
- Fibrinogen in plasma on Day 0, Day 30 Visit, Day 60 Visit, and Day 90 Visit.
- HbA1c in blood on Day 0 and Day 90 Visit.
- sICAM-1 in serum on Day 0, Day 6, Day 30 Visit, Day 60 Visit, and Day 90 Visit.
- WBC and platelet count in blood on Day 0, Day 6, Day 30 Visit, Day 60 Visit, and Day 90 Visit.
- 8-epi-PGF2 $\alpha$  and 11-DTX-B2 in 24 hour urine on Day 0, Day 5, Day 30 Visit, Day 60 Visit, and Day 90 Visit (expressed as concentration adjusted for creatinine).

- Body weight and waist circumference on Day -2 and Day 90 Visit.

The results along with the changes from baseline will be listed and summarized. In addition line graphs will be produced for product means (and 95% CI) over all timepoints.

The analysis will compare the results on Day 90 between the THS 2.2 Menthol and mCC arms, and between the THS 2.2 Menthol and SA arms for the FAS and PP set. An ANCOVA model will be used with terms for Baseline, sex, average daily mCC consumption over the last 4 weeks as reported during screening and randomization arm. No adjustment will be made for multiple comparisons.

Blood pressure, HbA1c, LDL, HDL, TG, TC, WBC, body weight and waist circumference will be analyzed in the regular scale. 8-epi-PGF2 $\alpha$ , 11-DTX-B2, sICAM will be analyzed in the logarithmic scale. Other risk markers will be logarithmically transformed prior to analysis if there is evidence of non-normality by means of Shapiro-Wilks test.

The SAS code will be the same as described in Section 12.6.1.1 “**Analysis of Biomarkers of Exposure for Primary Endpoints**”.

LS means for each product along with the difference (THS 2.2 Menthol - mCC) or ratio (THS 2.2 Menthol : mCC) and 95% CI will be presented in the tables along with a forest plot of the results.

If there are any 11-DTX-B2 assessments performed within 5 half-lives since the use of a concomitant medication affecting the production of 11-DTX-B2, the analysis will be repeated by excluding these assessments for both the PP Set and FAS

All tables, figures and analyses will be produced for the FAS and PP Set. Figures will be produced for the PP Set.

The data will be presented in the below outputs:

TFL number	Title
FIGURES	
15.1.2.2	Forest Plot of Statistical Analysis of Risk Markers – PP Set
15.1.2.3.1	Risk Markers Mean and 95% CI – PP Set
15.1.2.3.2	Risk Markers Mean and 95% CI – FAS
TABLES	
15.2.4.25.1	Analysis of Risk Markers – PP Set
15.2.4.25.1.1	Analysis of 11-DTX-B2 (units) Excluding Assessments within 5 Half-Lives of a Concomitant Medication Affecting 11-DTX-B2 Production – PP Set
15.2.4.25.2	Analysis of Risk Markers – FAS
15.2.4.25.2.1	Analysis of 11-DTX-B2 (units) Excluding Assessments within 5

TFL number	Title
	Half-Lives of a Concomitant Medication Affecting 11-DTX-B2 Production – FAS
15.2.4.26.1	Descriptive Statistics of Blood Pressure (mmHg) – PP Set
15.2.4.26.2	Descriptive Statistics of Blood Pressure (mmHg) – FAS 15.2.4.27.1
	Descriptive Statistics of hs-CRP (units), homocysteine (units), blood glucose (units), LDL (units), HDL (units), TG (units), and TC (units) – PP Set
15.2.4.27.2	Descriptive Statistics of hs-CRP (units), homocysteine (units), blood glucose (units), LDL (units), HDL (units), TG (units), and TC (units) – FAS
15.2.4.28.1	Descriptive Statistics of Fibrinogen (units) – PP Set
15.2.4.28.2	Descriptive Statistics of Fibrinogen (units) – FAS
15.2.4.29.1	Descriptive Statistics of HbA1c (units) – PP Set
15.2.4.29.2	Descriptive Statistics of HbA1c (units) – FAS
15.2.4.30.1	Descriptive Statistics of sICAM (units) – PP Set
15.2.4.30.2	Descriptive Statistics of sICAM (units) – FAS
15.2.4.31.1	Descriptive Statistics of Total WBC Count (units), Neutrophils Counts (units), Basophils Counts (Units), Eosinophils Counts (units), Lymphocytes Counts (units), Monocytes Counts (units) and Platelet Count (units) – PP Set
15.2.4.31.2	Descriptive Statistics of Total Total WBC Count (units), Neutrophils Counts (units), Basophils Counts (Units), Eosinophils Counts (units), Lymphocytes Counts (units), Monocytes Counts (units) and Platelet Count (units) – FAS
15.2.4.32.1	Descriptive Statistics of 8-epi-PGF2 $\alpha$ (units) and 11-DTX-B2 (units) – PP Set
15.2.4.32.1.1	Descriptive Statistics of 11-DTX-B2 (units) Excluding Assessments within 5 Half-Lives of a Concomitant Medication Affecting 11-DTX-B2 Production – PP Set
15.2.4.32.2	Descriptive Statistics of 8-epi-PGF2 $\alpha$ (units) and 11-DTX-B2 (units) – FAS
15.2.4.32.2.1	Descriptive Statistics of 11-DTX-B2 (units) Excluding Assessments within 5 Half-Lives of a Concomitant Medication Affecting 11-DTX-B2 Production – FAS
15.2.4.33.1	Descriptive Statistics of Body weight (kg) and waist circumference (cm) – PP Set
15.2.4.33.2	Descriptive Statistics of Body weight (kg) and waist circumference (cm) – FAS

TFL number	Title
LISTINGS	
15.3.3.1	Listing of Urinary Biomarkers
15.3.3.2	Listing of Bood, Plasma, Serum, and Exhaled Air Biomarkers
15.3.6.6	Listing of Clinical Chemistry Data, Shift, Changes from Baseline and CTCAE grades
15.3.6.7	Listing of Hematology Data Shift, Changes from Baseline and CTCAE grades
15.3.6.9	Listing of Vital Signs Data and Changes from Baseline

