7.5.2 Other assessments

7.5.2.1 Risk Markers

The following risk markers will be assessed in this study:

- Systolic and diastolic blood pressure, hs-CRP, fibrinogen, homocysteine, blood glucose, LDL, HDL, TG, TC, HbA1c, sICAM-1, WBC count, Apo A1, Apo B, 8-epi-PGF2 α , 11-DTX-B2, platelet count, weight, and waist circumference.

The assessment of systolic and diastolic blood pressure, blood glucose, TG, TC, platelet count, weight, and waist circumference will not be repeated because they are part of the safety parameters or clinical evaluation.

Selected risk markers will be evaluated at the following time points in at least 10-hour of fasting state conditions for the assessments which require blood, serum, or plasma:

- Systolic and diastolic blood pressure: to be evaluated as risk markers on Day 0, Day 6, Day 30 Visit (Day 30), Day 60 Visit (Day 60), and Day 90 Visit (Day 91). The results from vital signs on Day 0, Day 6, Day 30 Visit, Day 60 Visit, and Day 90 Visit will be used.
- hs-CRP, homocysteine, blood glucose, LDL, HDL, TG, TC in serum: to be evaluated as risk markers on Day 0, at Day 30 Visit (Day 31), Day 60 Visit (Day 61), and Day 90 Visit (Day 91). Samplings will be planned to measure hs-CRP, homocysteine, LDL, HDL at the mentioned timepoints. The results on blood glucose, TG, and TC from the safety laboratory panel on Day 0, Day 30 Visit, Day 60 Visit, and Day 90 Visit will be used.
- Fibrinogen in plasma: to be evaluated as risk markers on Day 0, Day 30 Visit (Day 31), Day 60 Visit (Day 61), and Day 90 Visit (Day 91). Samplings will be planned to measure fibrinogen at the mentioned timepoints.
- HbA1c in serum: to be evaluated as risk markers at Day 0, and Day 90 Visit (Day 91). Samplings will be planned to measure HbA1c at the mentioned timepoints.
- Apo A1 and Apo B in serum on Day 0, and Day 90 Visit. Samplings will be planned to measure Apo A1 and Apo B at the mentioned timepoints.
- sICAM-1 in serum: to be evaluated as risk markers on Day 0, Day 6, Day 30 Visit (Day 31), Day 60 Visit (Day 61), and Day 90 Visit (Day 91). Samplings will be planned to measure sICAM-1 at the mentioned timepoints.
- 8-epi-PGF2 α and 11-DTX-B2 in urine: to be evaluated as risk markers in 24-hour urine on Day 0, Day 5, on Day 30 Visit, Day 60 Visit, and Day 90 Visit and in 4-hour urine fraction in Day 90 Visit. Samplings will be planned to measure 8-epi-PGF2 α and 11-

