12.6.4 Inferential Analysis

For the secondary BoExp and selected risk markers, the hypothesis to be tested is the same as described in Section 12.5.4. This will be tested for secondary BoExp on Day 5, and if significant, on Day 90.

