  - Nicotine equivalents (NEQ) (expressed in quantity excreted and concentration adjusted for creatinine) in 24-hour urine from Day 1 to Day 5, Day 30 Visit, Day 60 Visit and Day 90 Visit.
  - Nicotine and cotinine in plasma from Day 1 to Day 4, Day 5, Day 30 Visit, Day 60 Visit, and Day 90 Visit.

5. To describe the pharmacokinetic (PK) profiles of nicotine and cotinine in smokers in a confinement setting switching from mCC to THS 2.2 Menthol as compared to smokers continuing to smoke mCC.

Endpoints:

- Peak (highest concentration value along the day) on Day 5.
- Time to peak (actual time when the peak was observed compared to the time of the first cigarette) on Day 5.
- Weighted average concentration over 24 hours on Day 5.

6. To describe the change in Cytochrome P450 1A2 (CYP1A2) enzymatic activity in smokers switching from mCC to THS 2.2 Menthol as compared to smokers continuing to smoke mCC and SA.

Endpoint:

- Molar metabolic ratio of paraxanthine (PX)/caffeine (CAF) in plasma on Day 5 and Day 90 Visit.

7. To determine the changes in lung function in smokers switching from mCC to THS 2.2 Menthol as compared to those continuing to smoke mCC.

Endpoint:

Full lung functions:

- Diffusion capacity for lung CO (DLCO).
- Rate constant for lung CO (KCO).
- Forced expiratory volume in 1 second (FEV1).
- Forced vital capacity (FVC).
- Vital capacity (VC) expressed as L.
- Total lung capacity (TLC).
- Forced residual volume (FRV).
- Inspiratory capacity (IC).
- Mid expiratory flow (25-75)

8. To monitor the safety profiles during the study.

Endpoints:

- AEs, SAEs and device events, including THS 2.2 Menthol malfunction and misuse.
- Respiratory symptoms: cough assessment by visual analogue scale (VAS), Likert scales, and one open question.
- Vital signs.
- Electrocardiogram (ECG).
- Clinical chemistry, hematology, and urine analysis safety panel.
- Physical examination.
- Concomitant medications.

9. To monitor selected risk markers in a confinement and ambulatory setting in smokers switching from mCC to THS 2.2 Menthol as compared to smokers continuing to smoke mCC and to SA.

Endpoints:

- Systolic and diastolic blood pressure on Day 6, Day 30 Visit, Day 60 Visit, and Day 90 Visit.
- High sensitive C-reactive protein (hs-CRP), homocysteine, blood glucose, low density lipoprotein (LDL), high density lipoprotein (HDL), triglycerides (TG), and total cholesterol (TC) in serum on Day 30 Visit, Day 60 Visit, and Day 90 Visit.

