- Fibrinogen in plasma on Day 30 Visit, Day 60 Visit, and Day 90 Visit.
- Hemoglobin A1c (HbA1c) in blood on Day 90 Visit.
- Apolipoprotein A1 (Apo A1) and Apolipoprotein B (Apo B) in serum on Day 90 Visit.
- Soluble inter-cellular adhesion molecule-1 (sICAM-1) in serum on Day 6, Day 30 Visit, Day 60 Visit, and Day 90 Visit.
- White blood cell (WBC count), including count of differentials, and platelet count in blood on Day 6, Day 30 Visit, Day 60 Visit, and Day 90 Visit.
- 8-epi-prostaglandin F2 $\alpha$  (8-epi-PGF2 $\alpha$ ) and 11-dehydro-thromboxane B2 (11-DTX-B2) in 24 hour urine on Day 5, Day 30 Visit, Day 60 Visit, and Day 90 Visit (expressed as quantity excreted and concentration adjusted for creatinine).
- Body weight and waist circumference on Day 90 Visit.

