- Urinary BoExp (expressed as quantity excreted and concentration adjusted for creatinine) in 24-hour urine collection.
- NEQ (expressed as quantity excreted and concentration adjusted for creatinine) in 24-hour urine collection.
- Selected risk markers (hs-CRP, homocysteine, blood glucose, LDL, HDL, TG, TC, fibrinogen, HbA1c, Apo A1, Apo B, sICAM-1, WBC count, platelet count, 8-epi-PGF2 $\alpha$ , 11-DTX-B2) in respective body matrix when available.

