### 12.6.3.10 BoExp in Subjects Quitting Smoking

The data to be followed for subjects who quit smoking are:

CO (ppm) in exhaled breath, COHb in blood (%), Urinary BoExp and NEQ (expressed as quantity excreted and concentration adjusted for creatinine) in 24 hour urine collection, hs-CRP, homocysteine, blood glucose, LDL, HDL, TG, TC, fibrinogen, HbA1c, sICAM-1, total white blood cell count, platelet count, 8-epi-PGF2 $\alpha$  and 11-DTX-B2.

These data will be plotted and summarized versus time since quitting for all subjects who quit smoking. The time since quitting will be rounded up to the nearest 30 days, such that a subject who quits before the Day 30 Visit will be assumed to have quit smoking for 30 days at the Day 30 Visit, 60 days at the Day 60 Visit and 90 days at the Day 90 Visit. Similarly a subject who quits smoking between the Day 30 Visit and the Day 60 Visit will be assumed to have quit smoking for 30 days at the Day 60 Visit and 60 days at the Day 90 Visit, and a subject who quits smoking between the Day 60 Visit and the Day 90 Visit will be assumed to have quit smoking for 30 days at the Day 90 Visit.

The data will be presented in the below outputs if more than 5 subjects quit smoking in the THS 2.2 Menthol or MCC arm in a separate Appendix of the CSR.

TFL number	Title
FIGURES	
15.1.2.29	Biomarkers of Exposure and Risk Markers in Subjects who Quit Smoking vs. Time Since Quitting Smoking Arithmetic Mean and 95% CI – Subjects Quitting THS and CC
TABLES	
15.2.4.69	Descriptive Statistics of Biomarkers of Exposure and Risk Markers in Subjects who Quit Smoking Summarized by Time Since Quitting Smoking – Subjects Quitting THS and CC

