## 16 APPENDICES

## 16.1 Study Assessments

### Table A1 Study Assessments (separate table [Table A2] shown for 24 hour urine collections)

	Screening	Confinement Period							Ambulatory Period					Safety Follow-up z		
		-2	-1	0	1	2	3	4	5	6 y	30	31	60	61	90	91
Study Day	-30 to -3	-2	-1	0	1	2	3	4	5	30	31	60	61	90	91	91 to 119
Intention to quit smoking in the next 6 months (prochaska 'Stage of Change questionnaire)	•	•								•		•		•		
Readiness to comply with study protocol: to abstain from smoking for up to 91 days	•	•														
Identification of mCC	•	•														
THS 2.2 Menthol demonstration	•															
THS 2.2 Menthol product test and readiness to use the product g		•														
Question on product Preference		•														
Collection of mCC butts for accountability			•	•	•	•	•	•	•							
Collection tobacco plugs of used Menthol Tobacco Sticks for further analysis					•	•	•	•	•	•		•		•		

	Screening	Confinement Period										Ambulatory Period						Safety Follow-up z
		-2	-1	0	1	2	3	4	5	6 y	30	31	60	61	90	91	91 to 119	
Study Day	-30 to -3	-2	-1	0	1	2	3	4	5	6 y	30	31	60	61	90	91	91 to 119	
Collection of empty/partially used Menthol Tobacco Stick for accountability											•		•		•			
CO breath test h		•	•	•	•	•	•	•	•	•		•		•	•			
B: BoExp in blood: COHb i		•	•	•	•	•	•	•	•	•		•		•	•	•		
B: BoExp to nicotine in plasma: nicotine, cotinine j			•	•	•	•	•	•	•	•		•		•	•			
U: Ames Mutagenicity (see Table A2)			•						•						•			
U:all urinary BoExp (primary and secondary, and BoExp to nicotine) j (see Table A2)		•	•	•	•	•	•	•	•		•		•		•			
U:all urinary BoExp in 4-hour fraction (primary and secondary, and BoExp to nicotine) (see Table A3)		•													•			
B:Risk markers: hs-CRP, fibrinogen, homocysteine, LDL, HDL k			•									•		•		•		
B: Risk Marker: sICAM-1 l				•						•		•		•		•		

	Screening	Confinement Period							Ambulatory Period					Safety Follow-up z			
									Day 30 Visit ± 5 days	Day 60 Visit ± 5 days	Day 60 Visit ± 5 days						
Study Day	-30 to -3	-2	-1	0	1	2	3	4	5	6 y	30	31	60	61	90	91	91 to 119
B: Risk Marker: HbA1c, Apo A1 and Apo B m				•												•	
U: Risk markers I 24-hour urine: 8-epi- PGF2 $\alpha$ and 11-DTX-B2 (see Table A2) n				•					•		•		•		•		

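### Apo A1 and Apo B are named secondary risk-marker endpoints, but the SAP's risk-marker analysis section omits them, so no summary or between-arm estimate is planned

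*SAP*

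**What the plan says.** Secondary objective 9 in SAP 5.2 begins "To monitor selected risk markers in a confinement and ambulatory setting in smokers switching from mCC to THS 2.2 Menthol" and sets the comparison against both continued mCC smoking and SA. One of its nine endpoint bullets is "Apolipoprotein A1 (Apo A1) and Apolipoprotein B (Apo B) in serum on Day 90 Visit". Protocol 3.4.2 carries the same endpoint.

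Protocol 7.5.2.1 schedules both markers for Day 0 and the Day 90 Visit: "Samplings will be planned to measure Apo A1 and Apo B at the mentioned timepoints". The protocol's time schedules for Day 0 and Day 91 (Tables 10 and 18) include them without restriction by arm. The SAP's own schedule (Table A1) still has the row "B: Risk Marker: HbA1c, Apo A1 and Apo B".

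On inference, Protocol 12.6.4 states: "For the secondary BoExp and selected risk markers, the hypothesis to be tested is the same as described in Section 12.5.4". It does not say which risk markers are meant.

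SAP 12.6.2.5 then enumerates the risk markers and specifies a Day 90 ANCOVA for THS 2.2 Menthol versus mCC and versus SA, on the FAS and PP Set. The list contains "HbA1c in blood on Day 0 and Day 90 Visit" and continues with sICAM-1. Apo A1 and Apo B are not in the list, the analysis-scale rules or the table titles.

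**The concern.** An endpoint named in the objectives and measured in every arm should have a matching analysis. Here the chain from objective to sampling to analysis breaks at the last step. SAP 12.1 says that summaries and analyses are presented only where the SAP details them, so silence in 12.6.2.5 is not neutral: read literally, it leaves the two markers in data listings only.

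At stake are two pre-specified secondary endpoints. If the gap is noticed only after database lock, SAP 13.4 would have any analysis of them identified in the study report as unplanned. That is a weaker standing than they were meant to have.

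**Working it through.** No sample size, power or alpha figure is involved. The check is a comparison of lists.

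**Objective against analysis list** (systolic and diastolic pressure counted separately; WBC differentials not counted)

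| Group | SAP 5.2, objective 9 | SAP 12.6.2.5 |
|---|---|---|
| Systolic and diastolic blood pressure | 2 | 2 |
| hs-CRP, homocysteine, glucose, LDL, HDL, TG, TC | 7 | 7 |
| Fibrinogen | 1 | 1 |
| HbA1c | 1 | 1 |
| **Apo A1, Apo B** | **2** | **0** |
| sICAM-1 | 1 | 1 |
| WBC, platelets | 2 | 2 |
| 8-epi-PGF2α, 11-DTX-B2 | 2 | 2 |
| Weight, waist circumference | 2 | 2 |
| **Total** | **20** | **18** |

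The difference, 20 − 18 = 2, is exactly Apo A1 and Apo B.

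**Scale rules in 12.6.2.5.** Untransformed: blood pressure (2), HbA1c, LDL, HDL, TG, TC, WBC, weight, waist = 10. Logarithmic: 8-epi-PGF2α, 11-DTX-B2, sICAM = 3. The residual group, governed by a Shapiro-Wilk check, takes what is left of the list: hs-CRP, homocysteine, glucose, fibrinogen, platelets = 5. The sum is 10 + 3 + 5 = 18, so the residual group has members without the apolipoproteins.

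**Descriptive tables.** Tables 15.2.4.26 to 15.2.4.33 form eight PP Set and FAS pairs, one for each of the eight bullets in the 12.6.2.5 list. None names Apo A1 or Apo B.

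**Other places they might be analysed.** They are not in the laboratory safety panel (SAP Table 27), nor in the sections on 4-hour urine or oxysterols.

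**Quitters analysis.** SAP 5.3 (objective 9) includes "fibrinogen, HbA1c, Apo A1, Apo B, sICAM-1, WBC count, platelet count"; SAP 12.6.3.10 has "fibrinogen, HbA1c, sICAM-1, total white blood cell count, platelet count". Counting the risk markers in full, 5.3 names 16 and 12.6.3.10 names 14. The same two are missing.

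**Record of a decision.** SAP Section 9 declares other removals, for example the analysis relating BoExp to NEQ and the use of quantity excreted in the 4-hour fraction. Neither it nor the revision history in 3.1 mentions dropping Apo A1 or Apo B.

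**Size of the repair.** 2 markers × 2 contrasts (mCC, SA) × 2 sets (FAS, PP Set) = 8 Day 90 ANCOVA contrasts, plus one pair of descriptive tables.

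**The case against.** The best reply is that the list does not fully control the output. It mentions only WBC and platelet counts, yet tables 15.2.4.31.1 and 15.2.4.31.2 also report the differential counts, which come from SAP 5.2. The analysis tables, forest plot and mean plots carry generic risk-marker titles. The scale rule for other risk markers could be stretched to cover the apolipoproteins. The detailed table shells are in a separate document not available here, and individual values would in any case be listed, since SAP 12.1 provides listings of all collected data.

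This has some force. A reader might infer that the comparison will never be made; the documents support only that it is not planned. The generic wording does not supply a plan, however. The residual scale group already has five listed members, each listed marker has a named descriptive table, and SAP 12.1 requires the SAP itself to detail what is summarised. A listing is not a between-arm comparison.

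The consequence is also limited. The objective is to monitor these markers, secondary endpoints carry no multiplicity adjustment (SAP 12.1.7), and the success criterion in SAP 5.5.2 does not involve them. The quitters outputs appear only if more than five subjects quit in the THS 2.2 Menthol or mCC arm, and then in an appendix to the study report.

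A second tempting inference is selective reporting, because SAP Section 9 discloses that the study team was accidentally unblinded. The documents do not support it. Section 9 says version 1.0 preceded the first subject's first visit and that changes since then are listed in 3.1. No entry there names a removal of these markers. If that log is complete, the gap was already in version 1.0. The version 3.0 entry on tables deleted after client review is too unspecific to date it otherwise, and version 1.0 is not available. Both markers also remain in SAP 5.2, SAP 5.3 and the schedule, which looks more like lists that were not reconciled than a decision to drop endpoints.

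**Conclusion.** The point holds as an internal inconsistency with a real consequence. Followed as written, the SAP provides no summary and no THS-mCC or THS-SA estimate for 2 of the 20 risk markers named under secondary objective 9, and the same 2 are missing from the 16 named for the quitters analysis. This rests on reading 12.6.2.5 together with the restriction in SAP 12.1, and on the table titles given in the SAP; the separate shells could contain more. When and why the omission arose is not shown, and no link to the unblinding is claimed. The primary analysis, the sample size and the type I error are untouched. It should be corrected, because two pre-specified endpoints otherwise have no planned analysis.

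**What to change.** In SAP 12.6.2.5:

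- Add a bullet for serum Apo A1 and Apo B at Day 0 and the Day 90 Visit.
- State their analysis scale, or confirm that the Shapiro-Wilk rule for the remaining risk markers applies to them.
- Include them in the Day 90 ANCOVA versus mCC and versus SA on the FAS and PP Set, reported in tables 15.2.4.25.1 and 15.2.4.25.2.
- Add a PP Set and FAS pair of descriptive tables, matching the other markers.

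In SAP 12.6.3.10, add both markers to the list so that it agrees with SAP 5.3.

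If leaving them out was intended, record and justify the removal in Section 9 instead, and bring 5.2 and 5.3 into line.

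The cost is a short wording change, 8 further model contrasts and two tables. Sampling and the ANCOVA are already specified, and neither sample size nor alpha changes.

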### 12.6.3 Exploratory Analysis

#### 12.6.3.1 Biomarkers of Exposure in 4 hour fraction

The BoExp MHBMA, 3-HPMA, S-PMA, Total NNAL, total 1-OHP, Total NNN, 4-ABP, 1-NA, 2-NA, o-tol, CEMA, HEMA, B[a]P, HMPMA, S-BMA, and NEQ (all analysed from a 4 hour fraction) at Day -1 and Day 91 will be described as reported in Section 12.1.3 “Descriptive Statistics”. The parameters will be analyzed as concentration adjusted for creatinine.

All BoExp will be analyzed in the log-scale.

BoExp on Day 90 will be analyzed using the same model described in Section 12.6.1.1 “Analysis of Biomarkers of Exposure for Primary Endpoints”. No adjustment will be made for multiple comparisons. LS means for each product along with the ratio (THS 2.2 Menthol : mCC) and 95% CI will be presented in the tables.

BoExp will also be examined to compare the reductions in THS 2.2 Menthol vs. SA using the same methodology as above for the PP Set.

All figures, summaries and analyses will be performed on the PP Set and presented in an Appendix of the CSR.

The data will be presented in the below outputs:

TFL number	Title
TABLES	
15.2.4.34	Analysis of Biomarkers of Exposure in 4-hour Fraction versus mCC and SA on Day 90 Visit- PP Set
15.2.4.35	Descriptive Statistics of MHBMA in 4-hour Urine Fraction – PP Set
15.2.4.36	Descriptive Statistics of 3-HPMA in 4-hour Urine Fraction – PP Set
15.2.4.37	Descriptive Statistics of S-PMA in 4-hour Urine Fraction – PP Set
15.2.4.38	Descriptive Statistics of Total NNAL in 4-hour Urine Fraction – PP Set
15.2.4.39	Descriptive Statistics of 1-OHP in 4-hour Urine Fraction – PP Set
15.2.4.40	Descriptive Statistics of Total NNN in 4-hour Urine Fraction – PP Set

TFL number	Title
15.2.4.41	Descriptive Statistics of 4-ABP in 4-hour Urine Fraction – PP Set
15.2.4.42	Descriptive Statistics of 1-NA in 4-hour Urine Fraction – PP Set
15.2.4.43	Descriptive Statistics of 2-NA in 4-hour Urine Fraction – PP Set
15.2.4.44	Descriptive Statistics of o-toluidine in 4-hour Urine Fraction – PP Set
15.2.4.45	Descriptive Statistics of CEMA in 4-hour Urine Fraction – PP Set
15.2.4.46	Descriptive Statistics of HEMA in 4-hour Urine Fraction – PP Set
15.2.4.47	Descriptive Statistics of B[a]P in 4-hour Urine Fraction – PP Set
15.2.4.48	Descriptive Statistics of HMPMA in 4-hour Urine Fraction – PP Set
15.2.4.49	Descriptive Statistics of S-BMA in 4-hour Urine Fraction – PP Set
15.2.4.50	Descriptive Statistics of NEQ in 4-hour Urine Fraction – PP Set
LISTINGS	
15.3.3.5	Listing of Biomarkers of Exposure in 4-hour Urine Fraction

